## 5.8.1.2. Liver Chemistry Monitoring Criteria

For subjects with ALT  $\ge 3x$  ULN **but** < 5x ULN **and** bilirubin < 2x ULN, without hepatitis symptoms or rash, and who can be monitored weekly for 4 weeks, the following actions should be taken:

- Notify the GSK Medical Monitor within 24 hours of learning of the abnormality to discuss subject safety
- Can continue study treatment
- Must return weekly for repeat liver chemistries (ALT, AST, alkaline phosphatase, bilirubin) until they resolve, stabilize or return to within baseline values
- If at any time the subject meets any of the liver chemistry stopping criteria 1-5, proceed as described above
- If, after 4 weeks of monitoring, ALT <3x ULN and bilirubin <2x ULN, monitor subjects twice monthly until liver chemistries normalize or return to within baseline values.

Refer to Appendix 1 for algorithm of liver chemistry monitoring, stopping and follow up criteria.

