#### Liver chemistry stopping criteria 1-5 are defined as follows:

1. ALT  $\ge 3x$  ULN and bilirubin  $\ge 2x$  ULN (>35% direct bilirubin) (or ALT  $\ge 3x$  ULN and INR > 1.5, if INR measured)

**NOTE:** If serum bilirubin fractionation is not immediately available, study drug should be discontinued if  $ALT \ge 3x$  ULN **and** bilirubin  $\ge 2x$  ULN. Serum bilirubin fractionation should be performed if testing is available. If testing is unavailable, **record presence of detectable urinary bilirubin on dipstick**, indicating direct bilirubin elevations and suggesting liver injury.

- 2. ALT > 5x ULN
- 3. ALT  $\geq$  3x ULN if associated with symptoms (new or worsening) believed to be related to hepatitis (such as fatigue, nausea, vomiting, right upper quadrant pain or tenderness, or jaundice) or believed to be related to hypersensitivity (such as fever, rash or eosinophilia).
- 4. ALT > 3x ULN persists for > 4 weeks
- 5. ALT  $\geq$  3x ULN and cannot be monitored weekly for 4 weeks

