### When any of the liver chemistry stopping criteria 1 - 5 is met, do the following:

- Immediately discontinue study treatment
- Report the event to GSK within 24 hours of learning its occurrence
- Complete the liver event CRF and SAE data collection tool if the event also meets the criteria for an SAE
  - All events of ALT ≥ 3x ULN and bilirubin ≥ 2x ULN (>35% direct bilirubin) (or ALT ≥3x ULN and INR > 1.5, if INR measured; INR measurement is not required and the threshold value stated will not apply to subjects receiving anticoagulants), termed 'Hy's Law', must be reported as an SAE (excluding studies of hepatic impairment or cirrhosis).
  - NOTE: if serum bilirubin fractionation is not immediately available, study treatment should be discontinued if ALT ≥ 3x ULN and bilirubin ≥ 2x ULN. Serum bilirubin fractionation should be performed if testing is available. If testing is unavailable, record presence of detectable urinary bilirubin on dipstick, indicating direct bilirubin elevations and suggesting liver injury.
- Complete the liver imaging and/or liver biopsy CRFs if these tests are performed
- Perform liver event follow up assessments, and monitor the subject until liver chemistries resolve, stabilize, or return to baseline values as described below
- Do not rechallenge with investigational product.

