#### 7.2.2.6. Prompt Reporting of SAEs and Other Events to GSK

SAEs, pregnancies, and liver function abnormalities meeting pre-defined criteria will be reported promptly by the investigator to GSK as described in the following table once the investigator determines the event meets the protocol definition for that event.

	Initial Reports	Reports Follow-up Information on a Previous Report		
Type of Event	Time Frame	Documents	Time Frame	Documents
All SAEs	24 hours	SAE data collection tool	24 hours	Updated SAE data collection tool
Pregnancy	2 Weeks	Pregnancy Notification Form	2 Weeks	Pregnancy Follow up Form
Liver chemistry abnorn	nalities:			
ALT≥3xULN and bilirubin≥1.5xULN (>35% direct) (or ALT≥3xULN and INR>1.5, if INR measured)³	24 hours 	SAE data collection tool. Liver Event Case Report Form (CRF) and liver imaging and/or biopsy CRFs if applicable 	24 hours	Updated SAE data collection tool. Updated Liver Event CRF 
ALT≥5xULN; ALT≥3xULN with hepatitis or rash or ALT ≥3xULN and <5xULN that persists ≥4 weeks	24 hours 	Liver Event CRF 	24 hours	Updated Liver Event CRF 
ALT≥3xULN and <5xULN and biliribin <1.5xULN	24 hours 	Liver Event CRF does not need completing unless elevations persist for 4 weeks or subject cannot be monitored weekly for 4 weeks 		

- 1. GSK to be notified at onset of liver chemistry elevations to discuss subject safety.
- 2. Liver event documents should be completed as soon as possible
- 3. INR measurement is not required; if measured, the threshold value stated will not apply to subjects receiving anticoagulants.

Methods for detecting, recording, evaluating, and following up on AEs and SAEs plus procedures for completing and transmitting SAE reports to GSK are provided in the SPM. Procedures for post-study AEs/SAEs are provided in the SPM.

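### In the protocol body text, a symptom-free subject first found with ALT ≥3x to <5xULN and bilirubin ≥2xULN that is known to be at most 35% direct meets no stopping rule and is excluded from the weekly liver-chemistry rule

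*Protocol*

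**What the plan says.** **Stopping rules (Protocol 5.8.1).**
- Criterion 1 pairs ALT of at least 3xULN with bilirubin of at least 2x "ULN (>35% direct bilirubin) (or ALT" of at least 3xULN with INR above 1.5). The INR limb is optional: "INR measurement is not required and the threshold value stated will not apply to subjects receiving anticoagulants". Where the fraction is missing the section is strict: "if serum bilirubin fractionation is not immediately available, study treatment should be discontinued if" ALT is at least 3xULN and total bilirubin at least 2xULN.
- Criterion 2 is ALT above 5xULN.
- Criterion 3 is ALT of at least 3xULN with symptoms attributed to hepatitis (jaundice is listed) or hypersensitivity.
- Criterion 4 is ALT above 3xULN for more than 4 weeks.
- Criterion 5 is ALT of at least "3x ULN and cannot be monitored weekly for 4 weeks".

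**Monitoring rule (5.8.1.2).** It applies when ALT is at least 3xULN but below "5x ULN and bilirubin < 2x ULN, without hepatitis symptoms or rash", and weekly attendance is possible. The Medical Monitor is told within 24 hours, treatment may go on, and chemistry is repeated weekly. The step-down to twice-monthly checks has its own bilirubin condition: "If, after 4 weeks of monitoring, ALT <3x ULN and bilirubin <2x ULN".

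**Reporting table (7.2.2.6).** Of its three liver rows:
- Row 1 begins "ALT≥3xULN and bilirubin≥1.5xULN (>35% direct", with INR above 1.5 as the alternative.
- Row 2 begins "ALT≥5xULN; ALT≥3xULN with hepatitis or rash" and adds ALT of 3x to <5xULN lasting at least 4 weeks.
- Row 3 is ALT of 3x to <5xULN with bilirubin below 1.5xULN.

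**Visit schedule (Table 3 and its note).** Chemistry, including direct bilirubin, is taken at every visit. Visits are weekly while the dose is unstable, may be 4-weekly after 3 stable weeks, and may be 6-weekly after three stable monthly visits. Section 5.8.1.2 refers to Appendix 1 for the algorithm, and that flowchart is not visible in the text available.

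**The concern.** The stopping rule and the monitoring rule should meet at bilirubin 2xULN, so that a subject who leaves one enters the other. They do not. The stopping rule looks at the direct fraction as well as the total, while the monitoring rule looks only at the total. A raised total with a low direct fraction drops between them.

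The result runs the wrong way. With the same ALT, the child with the lower bilirubin has mandatory weekly chemistry and 24-hour sponsor contact, and the child with the higher bilirubin has neither. If the investigator does not act on judgment, progression to a stopping criterion could be found at the next routine visit rather than within a week. This is a paediatric study whose primary endpoint is long-term safety.

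**Working it through.** There is no plan figure to reproduce. The check sets the rules side by side and then counts days.

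**1. A test case.** ALT 4xULN, bilirubin 2.5xULN, 20% direct, no symptoms or rash, INR not measured, newly found, able to attend weekly.

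| Rule | Requires | Met? |
|---|---|---|
| Criterion 1 | >35% direct, or fraction unavailable, or INR >1.5 | No |
| Criterion 2 | ALT >5xULN | No (4x) |
| Criterion 3 | Symptoms, including jaundice | No |
| Criterion 4 | ALT >3xULN for >4 weeks | No |
| Criterion 5 | Weekly monitoring impossible | No |
| 5.8.1.2 entry | Bilirubin <2xULN | No (2.5x) |
| 7.2.2.6 row 1 | >35% direct, or INR >1.5 | No |
| 7.2.2.6 row 2 | ALT ≥5xULN, hepatitis or rash, or ≥4 weeks | No |
| 7.2.2.6 row 3 | Bilirubin <1.5xULN | No |

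**2. The whole bilirubin range**, with everything else held as in the test case.

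| Bilirubin | Direct fraction | Stop (5.8.1) | Weekly rule (5.8.1.2) | 7.2.2.6 liver row |
|---|---|---|---|---|
| <1.5xULN | any | no | yes | 3 |
| 1.5x to <2xULN | >35% | no | yes | 1 |
| 1.5x to <2xULN | ≤35% | no | yes | none |
| ≥2xULN | >35% | criterion 1 | not needed | 1 |
| ≥2xULN | not available | stop on total | not needed | none, but an SAE under 7.2.2.2 |
| **≥2xULN** | **≤35%, known** | **no** | **no** | **none** |

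Only the last line is covered nowhere. It becomes covered if INR exceeds 1.5 (criterion 1), symptoms appear (criterion 3), ALT stays above 3xULN for more than 4 weeks (criterion 4) or weekly attendance is impossible (criterion 5). Criterion 4 can be recognised only by repeating the chemistry.

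**3. Dependence on order.** A child first found at bilirubin 1.8xULN enters the weekly rule. If bilirubin then rises to 2.5xULN with 20% direct, nothing in 5.8.1.2 takes the child out, and the step-down condition expects such values because it requires bilirubin to be back below 2xULN. A child first found at 2.5xULN never enters.

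**4. Size.** Assume a stable dose and a finding made at a scheduled visit (day 0), and use nominal days, ignoring the ±7-day window.

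- Next required chemistry under 5.8.1.2: day 7.
- 4-weekly schedule: day 28. Maximum delay 28 − 7 = 21 days. Checks not required: days 7, 14, 21, which is 3.
- 6-weekly schedule: day 42. Maximum delay 42 − 7 = 35 days. Checks not required: days 7, 14, 21, 28, 35, which is 5.
- Minimum delay in both: 0 days, if the investigator tests weekly anyway.
- Weekly schedule (unstable dose, including after any dose change): no chemistry lost.

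**The case against.** **The flowchart may settle it.** Section 5.8.1.2 sends the reader to Appendix 1, and content that is merely not visible cannot be called missing. This stands, and it limits the finding to the body text. If the flowchart does cover the case, the text still has to be aligned with it.

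**Other controls exist.** Section 4.2.1 requires permanent discontinuation for an adverse experience that the investigator judges an unacceptable risk, and also allows it at discretion. Section 7.2.1.1 allows more frequent visits on medical grounds. New jaundice believed related to hepatitis triggers criterion 3. A dose change made because of the result brings back weekly visits with chemistry. Footnote 1 to the 7.2.2.6 table asks for notification at onset with no bilirubin limit, though it is attached to the listed rows. Criterion 5 implies that anyone staying on drug with ALT ≥3xULN was meant to be seen weekly. All of this makes harm less likely and shows the intent. None of it orders a repeat test for this subject.

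**The case is narrow.** It needs a long run of conditions, plus an investigator who sees both values raised and does nothing. At most 12 children are enrolled. This stands and lowers the priority.

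**Indirect bilirubin may be left out on purpose.** A reader might infer that criterion 1 is itself wrong. The documents do not support that, since leaving mainly indirect bilirubin out of a stopping rule may be deliberate. That choice does not explain leaving the same subjects out of monitoring.

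**Conclusion.** The gap holds in the body text, for a symptom-free subject newly found with ALT ≥3x to <5xULN, bilirubin ≥2xULN, a known direct fraction ≤35%, INR unmeasured or ≤1.5, and weekly attendance possible. Direct bilirubin is in the routine panel, so the fraction would normally be known. The effect is a delay in the next required chemistry of 0 to 21 days on the 4-weekly schedule or 0 to 35 days on the 6-weekly schedule, and 24-hour contact that is not clearly required. How many subjects would show this pattern cannot be derived from the documents.

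Two stronger readings are tempting and not supported. One is that the protocol as a whole leaves such children unmonitored. Appendix 1 is not visible, and routine visits and investigator judgment remain. The other is that a delay of 3 or 5 weeks is to be expected. Those are maxima, reached only if the reduced schedule is kept in spite of the result. The priority is low: a safety clarification.

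**What to change.** 1. Check the Appendix 1 flowchart first, and align the text with it.
2. In 5.8.1.2, extend two actions only, the 24-hour Medical Monitor notification and the weekly repeat chemistry, to any subject with ALT ≥3xULN who meets no stopping criterion, whatever the bilirubin. This also catches ALT of exactly 5xULN, should criterion 2 really use a strict inequality.
3. Do not simply delete the bilirubin limit. That would carry the section's express permission to stay on treatment over to subjects with bilirubin ≥2xULN, which no liver provision now gives. For them, leave continuation to the investigator's risk judgment under 4.2.1, after discussion with the Medical Monitor.
4. Add a 7.2.2.6 row for ALT ≥3x to <5xULN with bilirubin ≥1.5xULN and ≤35% direct. The part from 1.5x to <2xULN already has weekly chemistry and notification under 5.8.1.2, so there the row only brings the table into line.

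Cost: a protocol amendment with IRB/IEC approval (section 10.2), and a few extra liver tests in an affected subject.

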# 6. CONCOMITANT MEDICATIONS AND NON-DRUG THERAPIES

## 6.1. Permitted Medications and Non-Drug Therapies

Any medication taken within 7 days of study medication administration must be recorded in the CRF.

All concomitant medications taken during the study will be recorded in the CRF with indication, dose information, as well as start and stop dates of administration.

If any medication is required at any time within 7 days before study treatment administration until completion of the 4-week follow-up visit, subjects should consult the investigator and details should be recorded in the CRF.

#### 6.1.1. Antacids and Vitamin/Mineral Supplements

Ingestion of polyvalent cation-containing antacids, and vitamin/mineral supplements (aluminum, calcium, iron, magnesium, selenium, strontium among others) with study treatment may result in a decrease in exposure of eltrombopag. Therefore, every effort must be made to educate subjects on how to take study treatment with these medications. Details of these and all concomitant medications should be recorded in the CRF

CONFIDENTIAL

Administration of eltrombopag, as the tablet or the PfOS formulation, with polyvalent metal cation-containing antacids or with high-calcium (425mg calcium) meals reduced plasma eltrombopag AUC(0-∞) and Cmax 60 to 80%. Administration of eltrombopag PfOS 2 hours after a high-calcium (425mg calcium) meal reduced plasma eltrombopag AUC(0-∞) and Cmax approximately 50%. Administration of eltrombopag PfOS 2 hours before a high-calcium (425mg calcium) meal attenuated the effect, resulting in plasma eltrombopag AUC(0-∞) and Cmax values 15 to 20% lower compared to fasting. Administration of eltrombopag with low-calcium (<50mg calcium) meals did not significantly alter plasma eltrombopag exposure. Given these data, the recommendations in the following sections (Section 6.1.1.1 and Section 6.1.1.2) for administration of eltrombopag relative to polyvalent metal cation-containing products such as some antacids, vitamin/mineral supplements, and dairy products should be followed.

#### 6.1.1.1. Antacids

Subjects requiring routine (e.g. daily) acid suppression should be encouraged to take H2 antagonists like ZANTACTM, Famox, Pepzan, Pepcidine, Axid or proton pump inhibitors like Losec, Nexium, Zoton, Protium.

Subjects requiring occasional acid suppression may take liquid or chewable antacids (TUMSTM, Maalox, Mylanta, Amphogel, Milk of Magnesia) provided study medication is taken at least 2 hours before or 4 hours after consumption of polyvalent cation containing antacids.

## **6.1.1.2.** Calcium and Vitamin/Mineral Supplements

Calcium and/or vitamin/mineral supplements as described above are permitted during the study but study treatment must be taken at least 2 hours before or 4 hours after consumption of these products.

#### 6.1.2. HMG-CoA Reductase Inhibitors (statins)

Subjects receiving HMG-CoA reductase (3-hydroxy-3-methyl-glutaryl-coenzyme A) inhibitors during the study should be closely monitored for safety, such as liver chemistry and signs and symptoms of myolysis, and efficacy, such as cholesterol and triglycerides (refer to individual product information for monitoring recommendations).

CONFIDENTIAL

Preclinical data showed that eltrombopag is an inhibitor of the transporters OATP1B1 and BCRP. Therefore, a clinical drug interaction study to evaluate the impact of eltrombopag on the PK of rosuvastatin, an OATP1B1 and BCRP substrate, was conducted in healthy subjects. Co-administration of eltrombopag 75 mg once daily for 5 days with a single 10 mg dose of rosuvastatin administered on Day 5 increased plasma rosuvastatin Cmax 2.03-fold and AUC( $0-\infty$ ) 55%. When co-administered with eltrombopag, a 50% dose reduction of the HMG-CoA reductase inhibitor is recommended.

Concomitant administration of eltrombopag and other OATP1B1 or BCRP substrates should be used with caution.

## 6.1.3. Concomitant ITP Therapy

Subjects will be permitted to use stable maintenance ITP therapy (including, but not limited to: corticosteroids, azathioprine, danazol, cyclosporine A, mycophenolate mofetil), as per local ITP treatment protocols.

Use of rescue ITP medication is allowed at any time the investigator deems it is indicated. Rescue medication is defined as the addition of new therapies intended to raise the platelet count, including medications, platelet transfusions, splenectomy or the increase of the dose of any concomitant ITP medications taken at baseline.

Concomitant ITP medications may be reduced at the discretion of the investigator according to the platelet count and provided the dose of eltrombopag has been stable for 3 consecutive weeks.

Investigators may use accepted local protocols or guidelines for reduction of concomitant ITP medications; however, the dose of eltrombopag should not be reduced while tapering concomitant ITP medications unless clinically indicated. Investigators must carefully document all concurrent medications received for treatment of ITP and any changes in dosage strength or frequency in the CRF.

## 6.2. Prohibited Medications and Non-Drug Therapies

Subjects must abstain from using investigational and prohibited prescription or non-prescription drugs within 7 days or 5 half-lives (whichever is longer) prior to the first dose of study treatment and until completion of follow-up procedures unless in the opinion of the Investigator and sponsor the medication will not interfere with the study (see Section 4.1 Subject Selection Criteria).

Drugs that affect platelet function (including but not limited to, aspirin, clopidogrel and/or NSAIDS) should not be taken during the study unless there is a very clear indication and the Investigator documents the rationale. This is due to the fact that they may affect the results of the bleeding scale assessments.

Any other TPO-R agonists are prohibited during the study.

Subjects must abstain from taking herbal supplements within 7 days (or 14 days if the drug is a potential enzyme inducer) or 5 half-lives (whichever is longer) prior to the first dose of study treatment until completion of the 4-week follow-up visit, unless the Investigator and medical monitor agree that the medication will not interfere with the study treatment.

# 6.3. Treatment after Discontinuation of Study Treatment or Withdrawal from/Completion of Study

The investigator is responsible for ensuring that consideration has been given for the post-study care of the patient's medical condition whether or not GSK is providing specific post-study treatment.

## 6.4. Treatment of Eltrombopag Overdose

Treatment of any suspected or confirmed overdose with eltrombopag should be symptomatic, and supportive care is recommended in cases where overdose is suspected, as per the IB for eltrombopag

No specific antidote is known. A hematologist will be consulted and appropriate treatments will be determined.

For the purposes of this study, an overdose of eltrombopag is defined as any dose greater than the highest daily dose included in the protocol.

#### 7. STUDY ASSESSMENTS AND PROCEDURES

A signed, written informed consent form must be obtained from the subject's guardian prior to any screening or study-specific procedures or assessments. Subjects over 6 years old will be asked to sign an assent form.

Subjects must be screened to ensure they meet the eligibility criteria specified in Section 4.1, Subject Selection Criteria. All screening and baseline evaluations must be completed prior to initiating treatment with study treatment.

Refer to the Time and Events Table for the timing of all assessments (Table 3). Details on safety assessments are presented in Section 7.2, respectively. Further details of study procedures and assessments can be found in the study procedures manual (SPM).

Weekly visits will take place within  $\pm 3$  days of the nominal visit date, in reference to Day 1. Monthly visits will take place within  $\pm 7$  days of the nominal visit date, in reference to Day 1. Every effort should be made to keep to the nominal schedule.

Procedures conducted as part of the subject's routine clinical management (e.g., blood count) and obtained prior to signing of informed consent may be used for screening or baseline purposes provided the procedure meets the protocol-defined requirements and has been performed in the timeframe required for the study.

Investigators may be requested to perform additional safety tests during the course of the study based on newly available data to ensure appropriate safety monitoring. Appropriate local regulatory and ethical approvals should be obtained before any additional testing is performed.

Table 3 Time and Events Table

TRA117366	Screening 		Open-	Label Trea	tment Perio	d	F	ollo	w-up	Perio	od .
Study Day		Day 1	Weekly	Every 4 weeks	Every 6 weeks	End of Treatment 	1W FU 		3W FU 	4W FU	
Informed consent	Х										
Medical history and evaluation of eligibility	Х										
Physical exam 	X										
Concurrent medication review		Х	Χ	Χ	Х	Χ	Χ	Χ	Χ	Χ	
Pregnancy test (urine) 		X5	At le	ast every 8	weeks					Χ	
CBC 6		Х	Χ	Χ	Х	Χ	Χ	Χ	Χ	Χ	
Peripheral blood smear 		Х	Χ	Χ	Х	Χ					
Clinical chemistry 		Χ	Χ	Χ	Х	Χ	Χ	X 9	X 9	X 9	
AE questioning		Χ	Χ	Χ	Х	Χ	Χ	Χ	Χ	Χ	
Cataract assessment 			Every 12 months								

#### Table 3 Time and Events Table (Continued)

W: week; FU: follow-up; M: month

Note: If the subject continues on a stable dose of eltrombopag for 3 consecutive weeks, also if at the day 1 patient received stable dose in TRA115450 for at least 3 consecutive weeks (without changes in concomitant ITP therapy), assessments may be scheduled every 4 weeks ( $\pm 7$  days of nominal visit day) rather than weekly. If the subject continues on a stable dose of eltrombopag for 3 consecutive monthly visits (without changes in concomitant ITP therapy), including any consecutive monthly visits in TRA115450 prior to coming into this study, assessments frequency may be further reduced and may be scheduled every 6 weeks ( $\pm 7$  days of nominal visit day). If the dose of eltrombopag is not stable, weekly visits ( $\pm 3$  days of nominal visit day) will be required.

- 1. Screening visit may occur on the same day as the Day 1 visit.
- 2. All subjects will attend the End of Treatment visit on the day of or within 3 days after the last dose of study treatment.
- 3. Subjects who continue on treatment with eltrombopag (i.e., non-study treatment) will not be required to attend the Week 1, 2 and 3 Follow-up visits.
- **4.** Physical Exam to be performed at screening.
- 5. For female subjects of child-bearing potential, a negative pregnancy test (urine or blood sample) MUST be obtained within 24 hours prior to the first dose. Tests to confirm that female subjects of childbearing potential are not pregnant will be conducted at least once every 8 weeks while receiving study treatment and after 4 weeks following completion or discontinuation of study treatment.
- **6.** CBC parameters: platelet count, hemoglobin, and WBC, .
- 7. Peripheral blood smear to be performed on Day 1 and at least once every 6 weeks, regardless of the visit schedule (weekly, 4-weekly or 6-weekly).
- **8.** Clinical Chemistry: Alkaline phosphatase, AST, ALT, total bilirubin, and direct bilirubin.
- 9. If clinical chemistry at follow-up week 1 is normal, no clinical chemistry will be measured at follow-up weeks 2, 3 and 4.
- 10. An age-appropriate standard of care exam will be performed to assess the presence of cataracts every 12 months while in the study treatment period.

